## 2.4. Group description

The following group description will be used for the demography, reactogenicity and immunogenicity analyses.

| Group order in tables | Group label in tables
(8 characters only) | Group definition for footnote |
|-----------------------|--|-------------------------------|
| 1                     | F4co10W                                      | F4co 10 µg + WFI              |
| 2                     | F4co30W                                      | F4co 30 µg + WFI              |
| 3                     | F4co90W                                      | F4co 90 µg + WFI              |
| 4                     | F4co10A                                      | F4co 10 µg + AS01B            |
| 5                     | F4co30A                                      | F4co 30 µg + AS01B            |
| 6                     | F4co90A                                      | F4co 90 µg + AS01B            |

| gsk
GlaxoSmithKline | Stu                | dy RAP           |
|------------------------|--------------------|------------------|
| Study Id: 108706       | Abbreviated Title: | PRO HIV-005      |
| Version: Draft version | ⊠ Final            | Date: 26SEP 2008 |

## 2.5. Interim safety analysis

Six interim analyses were planned for safety evaluation (see Section 5.6).

These analyses have been performed at the end of the 7-day follow-up period (Days 7 and 37) after each vaccine injection in a subset of 12 subjects and for each vaccine dose (10, 30 and 90  $\mu$ g).

Analysis has been done on uncleaned and blinded data. Individual data listings of the demographic and safety data (solicited/unsolicited AE, SAE, haematology and biochemistry values) have been provided to the SRT. Tables with the number of subjects responding to each stopping rules have been also provided.

No clinical report has been written.

As interim safety analyses have been already performed, description of tables and template will be not be part of a RAP.

Protocol forwarded that Final analysis would be performed in 2 steps:

- A first analysis was performed on all data up to and including month 2. These analyses were based on amendment 2 of the present document.
- A second analysis was planned for the report to be written at the end of the study (month 12). The analyses to be covered are detailed in this version of the RAP.

## 3. STATISTICAL METHODOLOGY AND ANALYSIS

## 3.1. Study cohorts and demography analysis

## 3.1.1. Study cohorts

The number and percentage of subjects included in each of the study cohorts, for both the Month 2 and thre Month 12 analyses, as well as the reason(s) for elimination will be presented.

The number of subjects who attended each study visit and the identification numbers of subjects who dropped out from the study along with the reason for withdrawal will be displayed per group for both study conclusions (month 2 and month 12). From an analysis perspective, a "drop-out" is any subject who did not come back for the concluding visit/contact foreseen in the protocol. A subject who returns for the concluding visit/contact foreseen in the protocol is considered to have completed the study. Reasons for drop-out from the study will also be summarised by group.

| gsk
GlaxoSmithKline | Stu                | dy RAP           |
|------------------------|--------------------|------------------|
| Study Id: 108706       | Abbreviated Title: | PRO HIV-005      |
| Version: Draft version | ⊠ Final            | Date: 26SEP 2008 |

The age at the first vaccination and the intervals between visits defined in the protocol should be followed as closely as possible. Subjects falling outside of these intervals will be reviewed and eventually excluded from the According-To-Protocol immunogenicity analysis:

| Interval                      | Length of interval (Days) |
|-------------------------------|---------------------------|
| Visit 2 $\rightarrow$ Visit 3 | 14 ± 2                    |
| Visit 2 $\rightarrow$ Visit 4 | 30 - 34                   |
| Visit 1 $\rightarrow$ Visit 5 | 180 ± 14                  |
| Visit 5 $\rightarrow$ Visit 7 | 180 ± 14                  |

The number and percentage of subjects out of these defined limits for the age and/or the intervals between visits will be described. The denominator used to calculate the percentage is the number of subjects present at the considered visits.

An overview of the number of vaccine doses received will be displayed (only for Month 2 analysis).

For each activity, the minimum and maximum dates over all vaccinated subjects will be presented.

## 3.1.2. Analysis of demographics/baseline characteristics

Demographic characteristics (age, gender, race) of each study cohort, for both the Month 2 and thre Month 12 analyses, will be tabulated.

The mean age (plus range and standard deviation) by gender of the enrolled subjects, as a whole, and per group, will be calculated , (only for Month 2 analysis).

## 3.2. Reactogenicity

## 3.2.1. Cohorts

The primary analysis will be based on the total vaccinated cohort. If the percent of enrolled subjects excluded from the ATP cohort for analysis of safety is more than 5%, a second analysis based on this ATP cohort will be performed to complement the Total analysis.

## 3.2.2. Handling of missing data

For the analysis of solicited symptoms, missing or non-evaluable measurements will not be replaced. Therefore the analysis of the solicited symptoms based on the

| gsk
GlaxoSmithKline | Study RAP          |                  |
|------------------------|--------------------|------------------|
| Study Id: 108706       | Abbreviated Title: | PRO HIV-005      |
| Version: Draft version | on 🛛 Final         | Date: 26SEP 2008 |

totalvaccinated cohort will include only subjects/doses with documented safety data (i.e.symptom screen/sheet completed).

For the analysis of unsolicited adverse events/serious adverse event/concomitant medication, all vaccinated subjects will be considered and subjects who did not report an event will be considered as subjects without an event.

## 3.2.3. Compliance

This analysis will be performed for Month 2 only.

The number of doses injected, the number of doses not given according-to-protocol, the number of symptom sheets (SS) transcribed for local and general symptoms and, the compliance for local and general symptoms will be tabulated. Compliance (%) is defined as the number of (local/general) symptom sheets completed divided by the number of doses administered for a specified group. The number of doses not given according-to-protocol is the number of doses administered at wrong site and/or side, or administered using a wrong route as compared to the protocol specifications.

## 3.2.4. All symptoms

This analysis will be performed for Month 2 only.

The percentage of subjects with at least one local AE (solicited and unsolicited), with at least one general AE (solicited and unsolicited) and with any AE during the solicited follow-up period (Day 0 to Day 6) will be tabulated with exact 95% confidence interval (CI) after each vaccine injection and overall.

The percentage of vaccine injections followed by at least one local AE (solicited and unsolicited), by at least one general AE (solicited and unsolicited) and by any AE will be tabulated, overall vaccination course, with exact 95% CI.

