## 3.2.5. Solicited symptoms

This analysis will be performed for Month 2 only.

The number and percentage of subjects reporting each individual solicited local and general AE during the solicited follow-up period will be tabulated with exact 95% CI.

The number and percentage of vaccine injections followed by each individual solicited local and general AE will be tabulated, overall vaccination course, with exact 95% CI.

| gsk
GlaxoSmithKline | Stu                | dy RAP           |
|------------------------|--------------------|------------------|
| Study Id: 108706       | Abbreviated Title: | PRO HIV-005      |
| Version: Draft version | ⊠ Final            | Date: 26SEP 2008 |

The maximum intensity of fever and local injection site redness/swelling will be scored as follows:

| Symptoms                       | Grade | Scale             |
|--------------------------------|-------|-------------------|
| Fever                          | 0     | ] 37.5°C          |
| (Oral or Axillary temperature) | 1     | [ 37.5°C – 38°C ] |
| . ,                            | 2     | ] 38°C – 39°C ]   |
|                                | 3     | [ 39°C            |
| Redness/Swelling               | 0     | 0 mmm             |
|                                | 1     | [ 20 mm           |
|                                | 2     | ]20 mm – 50 mm ]  |
|                                | 3     | ] 50 mm           |

The same tabulations will be done for grade 3 adverse events and/or for adverse events with relationship to vaccination.

The number and percentage of of subjects reporting a solicited symptom will be also presented by duration ( $\leq 2$  days or > 2 days).

For fever, temperatures will be also summarized in 0.5°C increments.

The number of days with a solicited symptom during the solicited follow-up period will be aslo presented. The same tabulations will be done for grade 3 adverse events and/or for adverse events with relationship to vaccination.

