## 3.4. Methodology for computing CI

All CI will be 2 sided 95% CI.

- The exact 95% CIs for a proportion within a group will be calculated from Proc StatXact [Clopper CJ, Pearson ES. The use of confidence or fiducial limits illustrated in the case of binomial. *Biometrika*. 1934;26:404-413].
- The 95% CI for geometric mean titers/concentrations (GMTs/GMCs) will be obtained within each group separately. The 95% CI for the mean of log-transformed titer/concentration will be first obtained assuming that log-transformed values were normally distributed with unknown variance. The 95% CI for the GMTs/GMCs will be then obtained by exponential-transformation of the 95% CI for the mean of log-transformed titer/concentration.

| gsk
GlaxoSmithKline | Stu                | Idy RAP          |  |
|------------------------|--------------------|------------------|--|
| Study Id: 108706       | Abbreviated Title: | PRO HIV-005      |  |
| Version: Draft version | i ⊠ Final          | Date: 26SEP 2008 |  |

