#### 5.3.2.2. All symptoms

Template Table R - 3

Incidence and nature of symptoms reported during the 7-day (Days 0-6) post-vaccination period

|              | Any Symptom  |   |   |   | General symptoms |      |   |   | Local symptoms |     |      |   |   |   |     |      |
|--------------|--------------|---|---|---|------------------|------|---|---|----------------|-----|------|---|---|---|-----|------|
|              | Group        | Ν | n | % | 95%              | 6 CI | Ν | n | %              | 95% | 6 CI | Ν | n | % | 95% | 6 CI |
|              |              |   |   |   | LL               | UL   |   |   |                | LL  | UL   |   |   |   | LL  | UL   |
| Dose 1       | [Each group] |   |   |   |                  |      |   |   |                |     |      |   |   |   |     |      |
| Dose 2       | [Each group] |   |   |   |                  |      |   |   |                |     |      |   |   |   |     |      |
| Overall/dose | [Each group] |   |   |   |                  |      |   |   |                |     |      |   |   |   |     |      |
| Overall/subj | [Each group] |   |   |   |                  |      |   |   |                |     |      |   |   |   |     |      |

For each dose and overall/subject:

N= number of subjects with at least one documented dose

n/%= number/percentage of subjects presenting at least one type of symptom whatever the study vaccine administered For overall/dose:

N= number of documented doses

n/%= number/percentage of doses followed by at least one type of symptom whatever the study vaccine administered 95% CI = exact 95% confidence interval, LL = Lower Limit, UL = Upper Limit

Data source = Appendix table IIA, Appendix table IIB

| gsk
GlaxoSmithKline | Study RAP          |                  |  |  |  |  |
|------------------------|--------------------|------------------|--|--|--|--|
| Study Id: 108706       | Abbreviated Title: | PRO HIV-005      |  |  |  |  |
| Version: Draft version | n 🛛 Final          | Date: 26SEP 2008 |  |  |  |  |
|                        |                    |                  |  |  |  |  |

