|               | Total     | All                    |                 |              |   |      |    |  |  |
|               |           | > 20                   |                 |              |   |      |    |  |  |

For each dose and overall/subject:

N= number of subjects with at least one documented dose

n/%= number/percentage of subjects reporting at least once the symptom

For Overall/dose:

N= number of documented doses

n/%= number/percentage of doses followed by at least one type of symptom

95%CI= Exact 95% confidence interval; LL = lower limit, UL = upper limit

Data source = Appendix table IIA

| gsk GlaxoSm | nithKline     | Study RAP          |                  |  |  |  |  |  |
|------------------------|---------------|--------------------|------------------|--|--|--|--|--|
| Study Id: 1            | 108706        | Abbreviated Title: | PRO HIV-005      |  |  |  |  |  |
| Version:               | Draft version | ⊠ Final            | Date: 26SEP 2008 |  |  |  |  |  |

Template Table R - 5

Incidence of solicited general symptoms reported during the 7-day (Days 0-6) post-vaccination period

|                |           |             |     | [Each group]                                |   |      |    |  |  |  |
|----------------|-----------|-------------|-----|---|---|------|----|--|--|--|
|                |           |             |     |   |   | 95 % | CI |  |  |  |
| Symptom        | Follow-up | Туре        | Ν   | n   | % | LL   | UL |  |  |  |
|                |           |             | [Ea | [Each dose]/Overall dose/Overall
subject |   |      |    |  |  |  |
| (Each symptom) | <= 2 days | All         |     |   |   |      |    |  |  |  |
|                |           | Grade 3     |     |   |   |      |    |  |  |  |
|                |           | Rel         |     |   |   |      |    |  |  |  |
|                |           | Rel*Grade 3 |     |   |   |      |    |  |  |  |
|                | > 2 days  | All         |     |   |   |      |    |  |  |  |
|                |           | Grade 3     |     |   |   |      |    |  |  |  |
|                |           | Rel         |     |   |   |      |    |  |  |  |
|                |           | Rel*Grade 3 |     |   |   |      |    |  |  |  |
|                | Total     | All         |     |   |   |      |    |  |  |  |
|                |           | Grade 3     |     |   |   |      |    |  |  |  |

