|                      |                       |                   |   |       |    |  |  |
|                      |                       |                   |   |       |    |  |  |
|                      |                       |                   |   |       |    |  |  |

At least one symptom = at least one symptom experienced (regardless of the MedDRA Preferred Term) N = number of administered doses

n/% = number/percentage of doses with the symptom

95% CI= exact 95% confidence interval; LL = Lower Limit, UL = Upper Limit

Data source = Appendix table IICi

#### Template Table R - 10

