#### 5.3.2.7. Concomitant medications

Template Table R - 14

Incidence of concomitant medication during the 30-day (Days 0-29) post-vaccination period

|  | [Each group] |   |   |    |    |  |  |
|--|--------------|---|---|----|----|--|--|
|  | 95% CI       |   |   |    |    |  |  |
|  | Ν            | n | % | LL | UL |  |  |
| [Each dose] [Overall/dose] [Overall/subject] |              |   |   |    |    |  |  |
| Any  |              |   |   |    |    |  |  |
| Any antibiotic                               |              |   |   |    |    |  |  |
| Any antipyretic                              |              |   |   |    |    |  |  |
| Any immunosuppressant                        |              |   |   |    |    |  |  |

For each dose and overall/subject:

N= number of subjects with at least one administered dose

n/%= number/percentage of subjects who started to take the specified concomitant medication at least once during the mentioned period

For overall/dose:

N= number of administered doses

n/%= number/percentage of doses after which the specified concomitant medication was started at least once during the mentioned period

95% CI = exact 95% confidence interval, LL = Lower Limit, UL = Upper Limit

Data source = Appendix table IIDi

| gsk
GlaxoSmithKline | Study RAP          |                  |  |  |  |
|------------------------|--------------------|------------------|--|--|--|
| Study Id: 108706       | Abbreviated Title: | PRO HIV-005      |  |  |  |
| Version: Draft version | ⊠ Final            | Date: 26SEP 2008 |  |  |  |

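### The exact 95% CIs on per-injection percentages treat a subject's two doses as independent, so they can cover less than 95% when a subject's responses are positively correlated

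*SAP*

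**What the plan says.** Two analyses pool injections over the vaccination course and attach an exact interval. SAP 3.2.4 covers injections followed by a local AE, a general AE or "by any AE will be tabulated, overall vaccination course, with exact 95% CI". SAP 3.2.5 adds: "The number and percentage of vaccine injections followed by each individual solicited local and general AE will be tabulated", again with an exact 95% CI. Protocol 10.7.3 asks for the same.

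The templates in SAP 5.3 make the dose the unit of analysis:

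- In the overall/dose rows of R-3, R-4, R-5 and R-7 the denominator is "N= number of documented doses". In R-4, for example, the numerator is "n/%= number/percentage of doses followed by at least one type of symptom".
- In R-9 every row is per dose: "n/% = number/percentage of doses with the symptom".
- In the overall/dose rows of R-14 the denominator is "N= number of administered doses".

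SAP 3.4 names one method for all of them: "The exact 95% CIs for a proportion within a group will be calculated from Proc StatXact", with the Clopper-Pearson reference. Neither document mentions within-subject correlation, clustering, a design effect or a robust interval.

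**The concern.** The Clopper-Pearson interval guarantees its level for independent trials with a common probability. Here each subject receives the same product up to twice and records both reactions on diary cards. If reactors tend to react again, two doses from one subject carry less information than two doses from two subjects. The effective sample size is then below the dose count, and the interval is narrower than its label allows.

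Reactogenicity is a primary endpoint. The per-dose rows also stand beside per-subject rows under the same interval label but with roughly twice the N, so they look more precise than the data may support. The each-dose and overall/subject rows count each subject once and are not affected.

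**Working it through.** **Inputs.** There are 50 subjects per AS01B group and 10 per WFI group (Protocol 6.4), with two vaccinations (SAP 2.1.2). With full compliance that is 50 × 2 = 100 or 10 × 2 = 20 doses per group. Intervals are two-sided 95% Clopper-Pearson (SAP 3.4). The within-subject correlation r is not in the documents, so it is an assumption shown over a range.

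**Model.** Let p be the event rate, the same at both doses. For one subject:

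- P(0 events) = (1−p)² + r·p(1−p)
- P(1 event) = 2p(1−p)(1−r)
- P(2 events) = p² + r·p(1−p)

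The variance of the subject's count is 2p(1−p)(1+r), against 2p(1−p) for independent doses, so the design effect is 1 + r. At p = 0.5 and r = 0.5 the three probabilities are 0.375, 0.25 and 0.375. With 100 doses the standard error of the percentage is √(0.25 × 1.5/100) = 6.1 points, where the binomial formula gives √(0.25/100) = 5.0.

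**Coverage.** The distribution of the total count is the convolution over 50 or 10 subjects. Coverage is the probability that the planned interval, computed with N = doses, contains p. No simulation is involved.

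| Subjects | Event rate | r = 0 | 0.1 | 0.2 | 0.3 | 0.5 | 0.7 |
|---|---|---|---|---|---|---|---|
| 50 | 2% | 98.5 | 97.9 | 97.5 | 97.0 | 96.1 | 95.1 |
| 50 | 5% | 98.3 | 97.7 | 97.0 | 96.3 | 94.7 | 92.4 |
| 50 | 10% | 95.6 | 94.5 | 93.3 | 92.2 | 89.8 | 87.4 |
| 50 | 20% | 96.7 | 95.8 | 94.9 | 93.9 | 91.9 | 89.8 |
| 50 | 50% | 96.5 | 95.5 | 94.5 | 93.5 | 91.4 | 89.3 |
| 50 | 70% | 96.3 | 95.3 | 94.2 | 93.2 | 91.0 | 88.9 |
| 10 | 10% | 98.9 | 98.4 | 98.0 | 97.6 | 96.8 | 95.8 |
| 10 | 20% | 97.8 | 97.2 | 96.4 | 95.5 | 93.3 | 90.5 |
| 10 | 30% | 97.5 | 96.8 | 95.9 | 95.1 | 93.2 | 91.5 |
| 10 | 50% | 95.9 | 94.8 | 93.6 | 92.5 | 90.1 | 87.9 |

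The r = 0 column reproduces the plan's stated level. With independent doses, coverage is at least 95.4% at every rate from 2% to 70% in one-point steps, for both group sizes. Any shortfall therefore comes from the correlation.

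For r from 0.3 to 0.7 on the same one-point steps:

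- 50 subjects, rates 10–70%: coverage 87.4–94.3%.
- 10 subjects, rates 20–70%: coverage 87.7–96.8%, with means of 94.4, 92.3 and 90.2% at r = 0.3, 0.5 and 0.7.

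**Width.** Apply Clopper-Pearson at effective N = doses/(1 + r), at an observed 50%.

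| Doses | Planned | r = 0.3 | r = 0.5 | r = 0.7 |
|---|---|---|---|---|
| 100 | 39.8–60.2 | 38.4–61.6 | 37.5–62.5 | 36.7–63.3 |
| 20 | 27.2–72.8 | 24.2–75.8 | 22.4–77.6 | 20.8–79.2 |

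The adjusted intervals are 14, 23 and 31% wider with 100 doses, and 13, 21 and 28% wider with 20.

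**The case against.** Five points can be made for the plan.

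- **Nothing is decided on these intervals.** The holding rules count subjects among the first 12 (Protocol 5.6.3), the planned models concern CD4+ responses (SAP 3.3.5.2), and valid each-dose and overall/subject intervals are in the same tables. This stands, and it limits the point to a minor one.
- **The correlation is assumed.** Clopper-Pearson is conservative and absorbs a small r. Averaged over event rates of 10–90%, coverage drops below 95% only between r = 0.1 and 0.2 with 50 subjects, and between 0.2 and 0.3 with 10. This stands: the direction is established, the size is not.
- **Many rows will be sparse.** R-9 is split by preferred term, and R-4 and R-5 by duration and severity. Sparse rows can keep 95%, as the table shows. This stands for those rows, but not for symptoms at moderate rates.
- **Rates may differ between doses.** Pooling unequal rates overstates the binomial variance and offsets part of the effect. With 50 subjects, rates of 20% and 60%, and r = 0.3 or 0.5, coverage is 95.0 or 93.3%, against 92.6 or 90.4% at a constant 40%. With rates of 10% and 30% it is 94.9 or 93.2%, against 93.9 or 91.9% at a constant 20%. The effect shrinks but remains at r = 0.5.
- **The timing is late.** SAP 3.2.4 to 3.2.6 are Month 2 analyses, and SAP 2.5 records that "A first analysis was performed on all data up to and including month 2". A new interval method would be chosen after that analysis. This is a good reason to prefer dropping the interval, which involves no choice of method.

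**Conclusion.** The concern holds, as a minor one. As written, the per-dose intervals carry a 95% label that the method does not guarantee when responses within a subject are positively correlated, and nothing in either document allows for that. For assumed correlations of 0.3 to 0.7, with full compliance and equal rates at both doses, coverage outside sparse rows is roughly 87 to 94% with 50 subjects and 88 to 97% with 10. For correlations of about 0.1 or less there is little or no loss. Point estimates, per-subject intervals, holding rules and the immunogenicity analyses are untouched.

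**What to change.** **Preferred.** Add one sentence to SAP 3.4: the overall/dose rows of R-3, R-4, R-5, R-7 and R-14, and all of R-9, show counts and percentages without a CI. Keep the exact intervals on the each-dose and overall/subject rows. Because Protocol 10.7.3 asks for the per-injection CI, record the change in SAP section 4.

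**Alternative, if an interval is wanted.** Use Clopper-Pearson at effective N = doses / design effect, with design effect = 1 + r × (2 × subjects with both doses / total doses) and r estimated from the data and truncated to 0–1. The SAP must name the estimator. One choice, for subjects with both doses, is r = 1 − d/[2p(1−p)], where d is the proportion with the event after exactly one dose and p is their per-dose event rate. Where r cannot be estimated (0% or 100% rows), use N = number of subjects. Exact enumeration of this rule with full compliance, at r = 0, 0.3, 0.5 and 0.7 and rates of 2–70%, gives coverage of at least 95.1% with 50 subjects. With 10 subjects the minimum is 94.0% after rounding (93.98%), and the mean is above 96% for both sizes. It is therefore close to nominal in the small groups, not guaranteed.

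**Cost.** The preferred change is one sentence and a table-format change. The alternative also needs some programming, and the intervals become about 13–31% wider at a 50% rate for r of 0.3–0.7. Either way, the affected Month 2 tables would have to be re-issued in the final report. A footnote saying that the intervals assume independent doses would be cheaper, but would leave the intervals uncorrected.
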